9.8.2 Staff Evaluations

Study staff should evaluate each unique memory aid entry according to “Toxicity Grading Scale for Healthy Adult and Adolescent Volunteers Enrolled in Preventive Vaccine Clinical Trials”, issued in September 2007 ([Appendix B: Toxicity Grading Scale](#)). Any memory aid entry determined to meet the criteria for a Grade 1 or higher adverse event must be documented as an adverse event. If the reminder memory aid entry does not meet the criteria of a Grade 1 or higher AE as per the toxicity grading scale, clinical judgment can be used to determine whether the entry should be recorded as an AE. For cases

where the reminder memory aid entry and final AE reporting (i.e., grading) do not agree, the reasoning must be recorded in the source documents.

The Investigational product administration procedure consists of insertion of the CELLECTRA™ 2000 5P-IM electroporation array needles (electrodes) through the skin and into the underlying muscle, and intramuscular injection of the Investigational product followed by delivery of the electroporation pulses. This procedure is broadly described as administration because it involves more than the injection of a drug. Attributing any reaction (e.g., pain, erythema, swelling) that is observed at or near the site of the Investigational product administration procedure to injection of the Investigational product or administration of the electroporation pulses will be difficult and is not necessary. Consequently, reactions arising from the Investigational product administration procedure may be reported as administration site or injection site reactions.

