When evaluating administration (injection) site reactions throughout the study, it is most important to be as specific as possible by selecting the most appropriate term (see [Table 5](#) below) and use the grading scale as listed in the Toxicity Grading Scale for Healthy Adult and Adolescent Volunteers Enrolled in Preventive Vaccine Clinical Trials, issued September 2007. Administration (injection) site reactions and administration site pain will be evaluated starting immediately and at 5 and 10 minutes following injection/EP. In addition, other events associated with administration (injection) site reactions (e.g., hematoma, infection or necrosis) should also be reported with preferred terms specific for administration (injection) site reactions. Injection site systemic and local reaction assessment that consists of evaluation of the following: General: hypotension, hyperhidrosis, erythema, headache, dizziness, myalgia, arthralgia, fever, peripheral edema, and local reaction: pain, pruritis, erythema, swelling, scab, infection. Non-injection site AEs will be assessed during the entire time while at the investigator site.

Table 5. Grading Scale for Injection Site Reactions

Local Reaction to Injectable Product (Grade)	Mild (1)	Moderate (2)	Severe (3)	Potentially Life Threatening (4)
Pain	Does not interfere with activity	Repeated use of non-narcotic pain reliever >24 hours or interferes with activity	Any use of narcotic pain reliever or prevents daily activity	Emergency room visit or hospitalization
Tenderness	Mild discomfort to touch	Discomfort with movement	Significant discomfort at rest	ER visit or hospitalization
Erythema/Redness ^a	2.5-5 cm	5.1-10 cm	>10 cm	Necrosis or exfoliative dermatitis
Induration/Swelling ^b	2.5-5 cm and no interference w/ activity	5.1-10 cm or interferes with activity	>10 cm or prevents daily activity	Necrosis

September 2007 “FDA Guidance for Industry—Toxicity Grading Scale for Healthy Adult and Adolescent Volunteers Enrolled in Preventive Vaccine Clinical Trials”

- In addition to grading the measured local reaction at the greatest single diameter, the measurement should be recorded as a continuous variable
- Should be evaluated and graded using the functional scale as well as the actual measurement.

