10.10 Dose Limiting Toxicity Criteria

Dose limiting toxicities are defined below for the purposes of evaluating the safety of the administered doses of dMAb AZD5396 and dMAb AZD8076. The following Investigational product administration-and/or EP- related adverse events are defined as DLTs:

- Grade 3 or greater local injection site erythema, swelling, and/or induration recorded \geq 1 hour after Investigational product administration
- Pain or tenderness at the injection site that requires overnight hospitalization despite proper use of non-narcotic analgesics.

- Grade 3 or greater systemic symptoms assessed by the Principal Investigator as related to Investigational product administration.
- Grade 3 or greater clinically significant laboratory abnormalities assessed by the Principal Investigator as related to Investigational product administration.

The most severe grade for that particular event is to be documented on the CRFs for DLT.

DLT assessment is scheduled for the first 3 to 6 participants for specified cohorts at Day 14 (Week2). Study Investigators are required to conduct clinical assessment and review blood test results performed. The DSMB is responsible for reviewing available safety data for specified cohorts. Refer to Section [4.2](#) for additional information on DLTs and the dose escalation scheme.

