15 APPENDICES

15.1 Appendix A: Participant Memory Aid

To be completed by Staff:

Participant ID: Site Number – Participant Number	Post-Vaccination  Day 0  Day 3
Today's date: dd/mm/yyyy	Timepoint:  Immediately after  5 minutes after  10 minutes after  Other: _____
Actual time: 24-hour clock	
VAS Pain Score: cm	
Administrator Comments: _____ _____ _____	

To be completed by Participant:

PAIN ASSESSMENT

Mark the line below using a single stroke at the point that you feel best represents the pain experienced related to the electrical pulses.

NO PAIN _____ WORST PAIN

Participant Reminder Diary

SARS-CoV-2-dMAB01

Subject #: _____

Injection Date: _____

Study Arm: _____

Note to Participant:

For questions or problems, please contact your Site Coordinator.

Name: _____

Telephone: () _____

Email (optional): _____

General Instructions

Temperature

Take your temperature orally around the same time each evening, using the thermometer provided and record it in the space provided. Also record the time at which you took your temperature. If you recently drank very hot or cold liquids, wait 15 minutes before taking your temperature.

Injection Site Symptoms

Pain and itching

Some people experience pain in the area where they were injected. Some people may also experience itching in the area where they were injected.

- By pain we mean that the place where you were injected hurts even when it isn't touched.

If you experience pain or itching at the injection site, use the following categories to describe how severe these symptoms were. If you don't experience one or more of these symptoms, mark the **NONE** box.

- **Mild** 😊 I only had a little discomfort. I could still use my arm like always.
- **Moderate** 😐 I noticed the discomfort and didn't use my arm as much as usual.
- **Severe** 😟 I really noticed the discomfort. It kept me from doing something I wanted or had to do.

Redness, swelling, and bruising

Some people experience redness, swelling, or bruising in the area where they were injected. If you experience redness, swelling, or bruising, measure the area using the measuring tool you were provided, and record the measurement in the space provided.

To measure the area of redness, swelling, or bruising, do the following:

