If you experience an injection site symptom, mark the box that describes your worst symptom until 11:59 p.m. tonight (Day 0). See General Instructions on page 2 for more information.

Symptom	None	Mild	Moderate	Severe
Pain				
Itching				

Redness, Swelling, or Bruising	None	Provide Maximum Measurement
Redness		cm at the longest part
Swelling		cm at the longest part
Bruising		cm at the longest part

Other Symptoms

If you experience symptoms other than the ones above, write them in the space below according to the General Instructions on page 2.

Did you experience any other symptoms? Yes No

Symptom or Medical Event	Mild	Moderate	Severe
			
			
			
			

Did you take any medications? Yes No

If yes, please list out the name(s) and dosage(s) below:

General Instructions

Temperature

Take your temperature orally around the same time each evening, using the thermometer provided and record it in the space provided. Also record the time at which you took your temperature. If you recently drank very hot or cold liquids, wait 15 minutes before taking your temperature.

Injection Site Symptoms

Pain and itching

Some people experience pain in the area where they were injected. Some people may also experience itching in the area where they were injected.

- By pain we mean that the place where you were injected hurts even when it isn't touched.

If you experience pain or itching at the injection site, use the following categories to describe how severe these symptoms were. If you don't experience one or more of these symptoms, mark the **NONE** box.

- **Mild** 😊 I only had a little discomfort. I could still use my arm like always.
- **Moderate** 😕 I noticed the discomfort and didn't use my arm as much as usual.
- **Severe** 😔 I really noticed the discomfort. It kept me from doing something I wanted or had to do.

Redness, swelling, and bruising

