Tenderness	Mild discomfort to touch	Discomfort with movement	Significant discomfort at rest	ER visit or hospitalization
Erythema/Redness *	2.5 – 5 cm	5.1 – 10 cm	> 10 cm	Necrosis or exfoliative dermatitis
Induration/Swelling **	2.5 – 5 cm and does not interfere with activity	5.1 – 10 cm or interferes with activity	> 10 cm or prevents daily activity	Necrosis

* In addition to grading the measured local reaction at the greatest single diameter, the measurement should be recorded as a continuous variable.

** Induration/Swelling should be evaluated and graded using the functional scale as well as the actual measurement.

Contains Nonbinding Recommendations

Vital Signs *	Mild (Grade 1)	Moderate(Grade 2)	Severe (Grade 3)	Potentially Life Threatening (Grade 4)
Fever (°C) ** (°F) **	38.0 – 38.4 100.4 – 101.1	38.5 – 38.9 101.2 – 102.0	39.0 – 40 102.1 – 104	> 40 ≥ 104
Tachycardia - beats per minute	101 – 115	116 – 130	> 130	ER visit or hospitalization for arrhythmia
Bradycardia - beats per minute***	50 – 54	45 – 49	< 45	ER visit or hospitalization for arrhythmia
Hypertension (systolic) - mm Hg	141 – 150	151 – 155	> 155	ER visit or hospitalization for malignant hypertension
Hypertension (diastolic) - mm Hg	91 – 95	96 – 100	> 100	ER visit or hospitalization for malignant hypertension
Hypotension (systolic) - mm Hg	85 – 89	80 – 84	< 80	ER visit or hospitalization for hypotensive shock
Respiratory Rate – breaths per minute	17 – 20	21 – 25	> 25	Intubation

* Subject should be at rest for all vital sign measurements.

** Oral temperature; no recent hot or cold beverages or smoking.

*** When resting heart rate is between 60 – 100 beats per minute. Use clinical judgement when characterizing bradycardia among some healthy subject populations, for example, conditioned athletes.

Systemic (General)	Mild (Grade 1)	Moderate(Grade 2)	Severe (Grade 3)	Potentially Life Threatening (Grade 4)
Nausea/vomiting	No interference with activity or 1 – 2 episodes/24 hours	Some interference with activity or > 2 episodes/24 hours	Prevents daily activity, requires outpatient IV hydration	ER visit or hospitalization for hypotensive shock
Diarrhea	2 – 3 loose stools or ≤ 400 gms/24 hours	4 – 5 stools or 400 – 800 gms/24 hours	6 or more watery stools or > 800gms/24 hours or requires outpatient IV hydration	ER visit or hospitalization

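### The diary records swelling by diameter alone and never prompts for hardness, so it cannot show a Grade 3 reaction reached through loss of function

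*Protocol*

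**What the plan says.** Appendix A has one diary page for each of Days 0 to 6, all with the same layout. For redness, swelling and bruising the instruction is to "measure the area using the measuring tool you were provided, and record the measurement in the space provided", and the answer is either None or a figure in "cm at the longest part". For pain and itching the participant is instead told to "use the following categories to describe how severe these symptoms were", with Mild, Moderate and Severe described by effect on use of the arm or on activity. General symptoms get the same three boxes. Induration (hardness) has no row.

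Table 5 (section 9.8.2) grades induration and swelling in one row. Grade 1 is 2.5-5 cm without interference with activity. Grade 2 is 5.1-10 cm, or interference. Grade 3 is more than 10 cm, or prevention of daily activity. Its footnote b reads "Should be evaluated and graded using the functional scale as well as the actual measurement", and Appendix B says the same: "Induration/Swelling should be evaluated and graded using the functional scale as well as the actual measurement".

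Section 9.8.2 links the two: "Study staff should evaluate each unique memory aid entry according to" the toxicity scale, with an adverse event mandatory from Grade 1. Section 10.10 lists first among the DLTs "Grade 3 or greater local injection site erythema, swelling, and/or induration recorded" at least one hour after administration, where related to the product or to electroporation.

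**The concern.** The grading rule needs two pieces of information about each swelling, and the home record asks for one. The missing piece can by itself make a reaction Grade 3, so a diary entry can look mild when the reaction meets a DLT criterion.

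Three uses of the data depend on that grade. Intensity of injection site reactions is part of the first primary safety endpoint (section 3.2). One DLT in the first three participants of a cohort brings an ad hoc DSMB review, and more than one in six means the dose is deemed not tolerated (section 4.2). The same Grade 3 event in two participants across cohorts meets a stopping rule (section 10.11). With three to six participants per cohort, one misgraded event can matter. An analysis plan cannot restore information that was never collected.

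**Working it through.** No sample size, power or interval calculation applies. The check is to grade each size band twice: once from the diary's cm field alone, and once from Table 5 with the effect on activity known.

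| Diameter | cm field alone | Table 5, interferes with activity | Table 5, prevents daily activity |
|---|---|---|---|
| under 2.5 cm | below Grade 1 | Grade 2 | Grade 3 |
| 2.5-5 cm | Grade 1 | Grade 2 | Grade 3 |
| 5.1-10 cm | Grade 2 | Grade 2 | Grade 3 |
| over 10 cm | Grade 3 | Grade 3 | Grade 3 |

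For swelling that prevents daily activity, the cm field falls short in all three bands up to 10 cm. For swelling that interferes without preventing, it falls short in the two bands up to 5 cm. Because Grade 1 also requires no interference, even an entry of 2.5-5 cm cannot be confirmed as Grade 1 from what it contains.

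Could another part of the diary supply the missing piece?

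- **Pain row.** A participant limited by swelling might tick Severe under Pain. That does not recover the DLT, because under section 10.10 pain or tenderness counts only if it requires overnight hospitalization.
- **Other symptoms.** The instruction is "If you experience symptoms other than the ones above, write them in the space below". Swelling is one of the symptoms above, so as worded this route is closed to it. Hardness could be written here with a severity box, but nothing prompts for it and no size is asked.
- **Measuring rule.** A swelling that falls between two circles takes the larger one. This can raise the recorded size, but says nothing about function.

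Could clinic visits supply it? Section 9.4.1 has the site assessed 30 minutes after injection and at each visit up to Day 10.

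- Cohorts A1 and A2 (three participants each in Table 2) have no scheduled visit between Day 0 and Day 7, so for Days 1 to 6 the diary is the only scheduled contemporaneous record.
- Cohorts B to G also have Days 3 and 10, which leaves shorter gaps. Cohort G has further checks at Days 28 and 31 and Weeks 5 and 6.
- The staff list of local reactions in sections 9.4.1 and 9.8.2 includes swelling but not induration, although section 10.10 names induration and Table 1 puts swelling, hardness or scabbing among reactions expected in at least 10%.

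**The case against.** The strongest reply is that the diary cell is not the final grade. Staff review the memory aid before anything reaches the CRF (section 9.8.1). They grade on a scale whose footnote already asks for function, may record an entry below Grade 1 as an adverse event, and may assign a grade that differs from the diary if the reason is documented (section 9.8.2). Participants are asked about injection site reactions at visits and told to report events immediately (section 9.7), and investigators make a clinical assessment for DLTs at Day 14 (section 10.10). Table 5 also treats induration and swelling as one row, and hardness can be entered under other symptoms.

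All of this stands, and it rules out two stronger readings. A reader might infer that a function-based Grade 3 swelling will be recorded as Grade 1 or 2, or as no adverse event. The documents do not support that, because staff have both the duty and the latitude to grade it correctly. A reader might also want to attach a probability that a cohort loses a DLT this way. The protocol gives no rate for swelling that limits activity. Its nearest figure, severe injection site pain or tenderness at 0.1% to under 1% (Table 1), concerns another reaction. Any assumed rate would give the chance that such an event occurs, not that it is missed.

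What the reply does not supply is a prompt. Nothing tells staff to ask about activity when they meet a swelling entry, so correct grading depends on the question being thought of and, for a reaction that has already resolved, on recall.

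**Conclusion.** The form and the grading rule do not match. From the diary alone, a swelling of 10 cm or less that prevents daily activity cannot be recognised as Grade 3, and hardness is not asked about at all. Such an event can be under-graded or missed unless staff happen to ask about function, mainly when it resolves between visits. The exposure is clearest on Days 1 to 6 in A1 and A2 and smaller in the other cohorts. The absence of a functional item can leave a grade unchanged or too low, never too high; rounding up to the larger circle is a separate effect on size.

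The size of the problem is therefore stated in grades (up to three steps: below Grade 1 against Grade 3) and not as a probability. The conclusion rests on the Appendix A pages as printed and on no separate form or staff instruction prompting for function. It is a modest point, worth acting on because the remedy is cheap and the missing information cannot be reliably recovered later.

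**What to change.** On each daily page of Appendix A, add activity boxes beside the swelling cm field, worded as in Table 5 (no interference, interferes, prevents daily activity). Add a hardness row with the same cm field and boxes. In section 9.8.2, have staff ask about effect on activity for every swelling or hardness entry at diary review and note the answer in source. No new grading sentence is needed, since footnote b already calls for both scales, and the DLT definition stays as written.

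The cost is one revised page template, one added instruction to staff, a slightly longer page for participants, and possibly a few more Grade 2-3 entries. No visits are added.

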15.2 Appendix B: Toxicity Grading Scale

Guidance for Industry

Toxicity Grading Scale for Healthy Adult and Adolescent Volunteers Enrolled in Preventive Vaccine Clinical Trials

Additional copies of this guidance are available from the Office of Communication, Training and Manufacturers Assistance (HFM-40), [name], or by calling [name] or [contact], or from the Internet at <http://www.fda.gov/cber/guidelines.htm>.

For questions on the content of this guidance, contact the Division of Vaccines and Related Products Applications, Office of Vaccines Research and Review at [contact].

**U.S. Department of Health and Human Services
Food and Drug Administration
Center for Biologics Evaluation and Research
September 2007**

Contains Nonbinding Recommendations

Table of Contents

I.	INTRODUCTION.....	1
II.	BACKGROUND.....	2
III.	TOXICITY GRADING SCALE TABLES.....	2
	A. Tables for Clinical Abnormalities	3
	B. Tables for Laboratory Abnormalities.....	6
IV.	REFERENCES.....	8

Contains Nonbinding Recommendations

Guidance for Industry

Toxicity Grading Scale for Healthy Adult and Adolescent Volunteers Enrolled in Preventive Vaccine Clinical Trials

This guidance represents the Food and Drug Administration's (FDA's) current thinking on this topic. It does not create or confer any rights for or on any person and does not operate to bind FDA or the public. You can use an alternative approach if the approach satisfies the requirements of the applicable statutes and regulations. If you want to discuss an alternative approach, contact the appropriate FDA staff. If you cannot identify the appropriate FDA staff, call the appropriate number listed on the title page of this guidance.

I. INTRODUCTION

Preventive vaccines are usually developed to prevent disease in a healthy population. The Office of Vaccines Research and Review, Center for Biologics Evaluation and Research, regulates preventive vaccines under authority of section 351 of the Public Health Service Act (42 U.S.C. 262), as well as specific sections of the Federal Food, Drug, and Cosmetic Act, and reviews investigational new drug applications (INDs) and biologics license applications (BLAs). (See, for example, Title 21 Code of Federal Regulations (CFR) Parts 312, 600, and 601). Most of the clinical trials of preventive vaccines conducted to support INDs and BLAs enroll healthy volunteers in all phases of vaccine testing. The enrollment of healthy volunteers warrants a very low tolerance for risk in those clinical trials.

This guidance provides you, sponsors, monitors, and investigators of vaccine trials, with recommendations on assessing the severity of clinical and laboratory abnormalities in healthy adult and adolescent volunteers enrolled in clinical trials. The grading system described in the table can also be useful in defining a particular study's stopping rules (e.g., a certain number of adverse events, as defined in the table, may call for stopping the study). Less extreme observations (e.g., mild) may not require discontinuing the study vaccine but can still contribute to evaluating safety by identifying parameters to focus upon in subsequent product development. Uniform criteria for categorizing toxicities in healthy volunteers can improve comparisons of safety data among groups within the same study and also between different studies. We, FDA, recommend using toxicity grading scale tables, provided below, as a guideline for selecting the assessment criteria to be used in a clinical trial of a preventive vaccine. We recommend incorporation of such appropriate, uniform, criteria into the investigational plan, case report forms, and study reports and correspondence with FDA, sponsors, monitors, investigators, and IRBs.

This guidance finalizes the draft guidance of the same title dated April 2005 (70 FR 22664, May 2, 2005).

Contains Nonbinding Recommendations

FDA's guidance documents, including this guidance, do not establish legally enforceable responsibilities. Instead, guidances describe FDA's current thinking on a topic and should be viewed only as recommendations, unless specific regulatory or statutory requirements are cited. The use of the word *should* in FDA's guidances means that something is suggested or recommended, but not required.

II. BACKGROUND

Standardized toxicity assessment scales have been widely used to evaluate products treating specific diseases. For example, the National Cancer Institute's Common Toxicity Criteria Scale and the Division of AIDS' Toxicity Grading Scale standardize the evaluation of adverse events among patients with cancer and HIV/AIDS, respectively (Refs. 1, 2). The defined toxicity parameters in those scales are designed for patients who may already experience mild, moderate, or severe adverse clinical or laboratory events due to the disease process, and may not be appropriate for healthy volunteers.

In the development of the toxicity grading scales for healthy volunteers, we chose parameter limit values based on published information, when such values were available (Refs. 1-6). For example, the Brighton Collaboration has developed case definitions and guidelines to evaluate some adverse events associated with administering vaccines (Ref. 3). In some cases, parameter limit values were based on clinical experience and experience reviewing vaccine clinical trials that enroll normal healthy subjects.

Toxicity grading scales for laboratory abnormalities should consider the local laboratory reference values when the parameter limit values are defined. The characterization of laboratory parameters among some populations of healthy adults and adolescents may require the exercise of clinical judgment, for example, consideration of the potential for ethnic differences in white blood cell (WBC) counts or gender differences in creatine phosphokinase (CPK) values.

III. TOXICITY GRADING SCALE TABLES

Adverse events in a clinical trial of an investigational vaccine must be recorded and monitored and, when appropriate, reported to FDA and others involved in an investigation (sponsors, IRBs, and investigators). (See, for example, 21 CFR 312.32, 312.33, 312.50, 312.55, 312.56, 312.60, 312.62, 312.64, 312.66). Although the use of a toxicity grading scale for adverse events would not replace these regulatory requirements, using a scale to categorize adverse events observed during a clinical trial may assist you in monitoring safety and making required reports. Nonetheless, we believe that categorization or grading of data as outlined in this document is supplementary to and should not replace full and complete data analysis.

These guidelines for toxicity grading scales are primarily intended for healthy adult and adolescent volunteers. The parameters in the tables below are not necessarily applicable to every clinical trial of healthy volunteers. The parameters monitored should be appropriate for the specific study vaccine. For some preventive vaccines under development, it may be appropriate

Contains Nonbinding Recommendations

to include additional parameters to be monitored during a clinical trial or to alter the choice of values in the toxicity table. For example, additional parameters might be added based on one or more of the following: safety signals observed in pre-clinical toxicology studies, the biological plausibility of the occurrence of certain adverse events, or previous experience with a similar licensed product.

As discussed above, the tables do not represent a recommendation to monitor all the listed parameters in all clinical trials of healthy volunteers, nor do the tables represent all possible parameters to be monitored. In addition, these tables do not represent study inclusion or exclusion criteria. We recommend that the parameters monitored be appropriate for the study vaccine administered to healthy volunteers participating in the clinical trial.

A. Tables for Clinical Abnormalities

Local Reaction to Injectable Product	Mild (Grade 1)	Moderate(Grade 2)	Severe (Grade 3)	Potentially Life Threatening (Grade 4)
Pain	Does not interfere with activity	Repeated use of non-narcotic pain reliever > 24 hours or interferes with activity	Any use of narcotic pain reliever or prevents daily activity	Emergency room (ER) visit or hospitalization
Tenderness	Mild discomfort to touch	Discomfort with movement	Significant discomfort at rest	ER visit or hospitalization
Erythema/Redness *	2.5 – 5 cm	5.1 – 10 cm	> 10 cm	Necrosis or exfoliative dermatitis
Induration/Swelling **	2.5 – 5 cm and does not interfere with activity	5.1 – 10 cm or interferes with activity	> 10 cm or prevents daily activity	Necrosis

* In addition to grading the measured local reaction at the greatest single diameter, the measurement should be recorded as a continuous variable.

** Induration/Swelling should be evaluated and graded using the functional scale as well as the actual measurement.

Contains Nonbinding Recommendations

Vital Signs *	Mild (Grade 1)	Moderate(Grade 2)	Severe (Grade 3)	Potentially Life Threatening (Grade 4)
Fever (°C) ** (°F) **	38.0 – 38.4 100.4 – 101.1	38.5 – 38.9 101.2 – 102.0	39.0 – 40 102.1 – 104	> 40 ≥ 104
Tachycardia - beats per minute	101 – 115	116 – 130	> 130	ER visit or hospitalization for arrhythmia
Bradycardia - beats per minute***	50 – 54	45 – 49	< 45	ER visit or hospitalization for arrhythmia
Hypertension (systolic) - mm Hg	141 – 150	151 – 155	> 155	ER visit or hospitalization for malignant hypertension
Hypertension (diastolic) - mm Hg	91 – 95	96 – 100	> 100	ER visit or hospitalization for malignant hypertension
Hypotension (systolic) - mm Hg	85 – 89	80 – 84	< 80	ER visit or hospitalization for hypotensive shock
Respiratory Rate – breaths per minute	17 – 20	21 – 25	> 25	Intubation

* Subject should be at rest for all vital sign measurements.

** Oral temperature; no recent hot or cold beverages or smoking.

*** When resting heart rate is between 60 – 100 beats per minute. Use clinical judgement when characterizing bradycardia among some healthy subject populations, for example, conditioned athletes.

Systemic (General)	Mild (Grade 1)	Moderate(Grade 2)	Severe (Grade 3)	Potentially Life Threatening (Grade 4)
Nausea/vomiting	No interference with activity or 1 – 2 episodes/24 hours	Some interference with activity or > 2 episodes/24 hours	Prevents daily activity, requires outpatient IV hydration	ER visit or hospitalization for hypotensive shock
Diarrhea	2 – 3 loose stools or ≤ 400 gms/24 hours	4 – 5 stools or 400 – 800 gms/24 hours	6 or more watery stools or > 800gms/24 hours or requires outpatient IV hydration	ER visit or hospitalization
Headache	No interference with activity	Repeated use of non-narcotic pain reliever > 24 hours or some interference with activity	Significant; any use of narcotic pain reliever or prevents daily activity	ER visit or hospitalization
Fatigue	No interference with activity	Some interference with activity	Significant; prevents daily activity	ER visit or hospitalization
Myalgia	No interference with activity	Some interference with activity	Significant, prevents daily activity	ER visit or hospitalization

Contains Nonbinding Recommendations

Systemic Illness	Mild (Grade 1)	(Moderate(Grade 2)	Severe (Grade 3)	Potentially Life Threatening (Grade 4)
Illness or clinical adverse event (as defined according to applicable regulations)	No interference with activity	Some interference with activity not requiring medical intervention	Prevents daily activity and requires medical intervention	ER visit or hospitalization

Contains Nonbinding Recommendations
B. Tables for Laboratory Abnormalities

The laboratory values provided in the tables below serve as guidelines and are dependent upon institutional normal parameters. Institutional normal reference ranges should be provided to demonstrate that they are appropriate.

Serum *	Mild (Grade 1)	Moderate (Grade 2)	Severe (Grade 3)	Potentially Life Threatening (Grade 4)**
Sodium - Hyponatremia mEq/L	132 - 134	130 - 131	125 - 129	< 125
Sodium - Hypernatremia mEq/L	144 - 145	146 - 147	148 - 150	> 150
Potassium - Hyperkalemia mEq/L	5.1 - 5.2	5.3 - 5.4	5.5 - 5.6	> 5.6
Potassium - Hypokalemia mEq/L	3.5 - 3.6	3.3 - 3.4	3.1 - 3.2	< 3.1
Glucose - Hypoglycemia mg/dL	65 - 69	55 - 64	45 - 54	< 45
Glucose - Hyperglycemia				Insulin requirements or hyperosmolar coma
Fasting - mg/dL	100 - 110	111 - 125	> 125	
Random - mg/dL	110 - 125	126 - 200	> 200	
Blood Urea Nitrogen BUN mg/dL	23 - 26	27 - 31	> 31	Requires dialysis
Creatinine - mg/dL	1.5 - 1.7	1.8 - 2.0	2.1 - 2.5	> 2.5 or requires dialysis
Calcium - hypocalcemia mg/dL	8.0 - 8.4	7.5 - 7.9	7.0 - 7.4	< 7.0
Calcium - hypercalcemia mg/dL	10.5 - 11.0	11.1 - 11.5	11.6 - 12.0	> 12.0
Magnesium - hypomagnesemia mg/dL	1.3 - 1.5	1.1 - 1.2	0.9 - 1.0	< 0.9
Phosphorous - hypophosphatemia mg/dL	2.3 - 2.5	2.0 - 2.2	1.6 - 1.9	< 1.6
CPK - mg/dL	1.25 - 1.5 x ULN***	1.6 - 3.0 x ULN	3.1 - 10 x ULN	> 10 x ULN
Albumin - Hypoalbuminemia g/dL	2.8 - 3.1	2.5 - 2.7	< 2.5	--
Total Protein - Hypoproteinemia g/dL	5.5 - 6.0	5.0 - 5.4	< 5.0	--
Alkaline phosphate - increase by factor	1.1 - 2.0 x ULN	2.1 - 3.0 x ULN	3.1 - 10 x ULN	> 10 x ULN
Liver Function Tests -ALT, AST increase by factor	1.1 - 2.5 x ULN	2.6 - 5.0 x ULN	5.1 - 10 x ULN	> 10 x ULN
Bilirubin - when accompanied by any increase in Liver Function Test increase by factor	1.1 - 1.25 x ULN	1.26 - 1.5 x ULN	1.51 - 1.75 x ULN	> 1.75 x ULN
Bilirubin - when Liver Function Test is normal; increase by factor	1.1 - 1.5 x ULN	1.6 - 2.0 x ULN	2.0 - 3.0 x ULN	> 3.0 x ULN
Cholesterol	201 - 210	211 - 225	> 226	--
Pancreatic enzymes - amylase, lipase	1.1 - 1.5 x ULN	1.6 - 2.0 x ULN	2.1 - 5.0 x ULN	> 5.0 x ULN

* The laboratory values provided in the tables serve as guidelines and are dependent upon institutional normal parameters. Institutional normal reference ranges should be provided to demonstrate that they are appropriate.

** The clinical signs or symptoms associated with laboratory abnormalities might result in characterization of the laboratory abnormalities as Potentially Life Threatening (Grade 4). For example, a low sodium value that falls within a grade 3 parameter (125-129 mEq/L) should be recorded as a grade 4 hyponatremia event if the subject had a new seizure associated with the low sodium value.

***ULN" is the upper limit of the normal range.

Contains Nonbinding Recommendations

Hematology *	Mild (Grade 1)	Moderate (Grade 2)	Severe (Grade 3)	Potentially Life Threatening (Grade 4)
Hemoglobin (Female) - gm/dL	11.0 – 12.0	9.5 – 10.9	8.0 – 9.4	< 8.0
Hemoglobin (Female) change from baseline value - gm/dL	Any decrease - 1.5	1.6 – 2.0	2.1 – 5.0	> 5.0
Hemoglobin (Male) - gm/dL	12.5 – 13.5	10.5 – 12.4	8.5 – 10.4	< 8.5
Hemoglobin (Male) change from baseline value - gm/dL	Any decrease - 1.5	1.6 – 2.0	2.1 – 5.0	> 5.0
WBC Increase - cell/mm ³	10,800 – 15,000	15,001 – 20,000	20,001 – 25,000	> 25,000
WBC Decrease - cell/mm ³	2,500 – 3,500	1,500 – 2,499	1,000 – 1,499	< 1,000
Lymphocytes Decrease - cell/mm ³	750 – 1,000	500 – 749	250 – 499	< 250
Neutrophils Decrease - cell/mm ³	1,500 – 2,000	1,000 – 1,499	500 – 999	< 500
Eosinophils - cell/mm ³	650 – 1500	1501 – 5000	> 5000	Hypereosinophilic
Platelets Decreased - cell/mm ³	125,000 – 140,000	100,000 – 124,000	25,000 – 99,000	< 25,000
PT – increase by factor (prothrombin time)	1.0 – 1.10 x ULN ^{***}	1.11 – 1.20 x ULN	1.21 – 1.25 x ULN	> 1.25 x ULN
PTT – increase by factor (partial thromboplastin time)	1.0 – 1.2 x ULN	1.21 – 1.4 x ULN	1.41 – 1.5 x ULN	> 1.5 x ULN
Fibrinogen increase - mg/dL	400 – 500	501 – 600	> 600	--
Fibrinogen decrease - mg/dL	150 – 200	125 – 149	100 – 124	< 100 or associated with gross bleeding or disseminated intravascular coagulation (DIC)

* The laboratory values provided in the tables serve as guidelines and are dependent upon institutional normal parameters. Institutional normal reference ranges should be provided to demonstrate that they are appropriate.

** "ULN" is the upper limit of the normal range.

Urine *	Mild (Grade 1)	Moderate (Grade 2)	Severe (Grade 3)	Potentially Life Threatening (Grade 4)
Protein	Trace	1+	2+	Hospitalization or dialysis
Glucose	Trace	1+	2+	Hospitalization for hyperglycemia
Blood (microscopic) – red blood cells per high power field (rbc/hpf)	1 – 10	11 – 50	> 50 and/or gross blood	Hospitalization or packed red blood cells (PRBC) transfusion

* The laboratory values provided in the tables serve as guidelines and are dependent upon institutional normal parameters. Institutional normal reference ranges should be provided to demonstrate that they are appropriate.

Contains Nonbinding Recommendations

IV. REFERENCES

1. National Cancer Institute Common Toxicity Criteria, April 30, 1999.
(<http://ctep.cancer.gov/reporting/CTC-3.html>)
2. Division of AIDS Table for Grading Severity of Adult Adverse Experiences; August 1992.
(http://rcc.tech-res-intl.com/tox_tables.htm)
3. The Brighton Collaboration. Finalized Case Definitions and Guidelines.
(http://brightoncollaboration.org/internet/en/index/definition_guidelines.html)
4. HIV Vaccine Trials Network Table for Grading Severity of Adverse Experiences; September 18, 2002. (http://rcc.tech-res-intl.com/tox_tables.htm)
5. Division of AIDS Table for Grading the Severity of Adult and Pediatric Adverse Events, December 2004.
(<http://www3.niaid.nih.gov/research/resources/DAIDSClinRsrch/PDF/Safety/DAIDSAEGradingTable.pdf>)

